STRESS AND IMMUNE RESPONSES DURING PREGNANCY

I. OBJECTIVES

This study will examine effects of everyday life stress and obesity on immune responses to influenza virus vaccine (the flu shot) during pregnancy. Antibody levels increase after vaccination. Higher antibody levels indicate better immune protection from influenza (the flu). In addition to providing protection from the flu for the mother, being vaccinated during pregnancy may protect infants from the flu during the first six months of life during which time infants cannot be vaccinated. Our goal is to determine whether greater life stress and obesity reduce 1) antibody responses to the flu shot in women and 2) antibody levels in the newborn at the time of delivery.

II. BACKGROUND AND SIGNIFICANCE

Stress and Antibody Response to Influenza Vaccination

Evidence supports an association between stress and poorer antibody response to influenza vaccination. In a sample of older adults, individuals who were caregiving for a spouse with dementia (a chronically stressed group) showed poorer response to influenza vaccine than control subjects matched for age, sex, and socioeconomic status ¹. Subsequent replication of these findings showed that both former caregivers (who had lost their spouses within the past few years) and current caregivers showed less antibody in response to vaccination than did control subjects ². Similarly, Vedhara et al. ³ found that caregiver stress was associated with poorer response to influenza vaccine; caregivers were less likely to show a four-fold increase in antibody production than were non-caregivers. Furthermore, Vedhara et al. (1999) found that among individuals showing adequate response, non-caregivers showed a more robust response. Many studies of the effects of stress on influenza vaccine to date have focused on older populations. However, stress has also affects immune response to influenza vaccination in a younger groups^{4 5}. Similarly, academic stress has been shown to affect antibody response to Hepatitis B vaccination in medical students, also a younger population ^{6 7}. To our knowledge, no study has explored the effects of stress on response to any vaccine during pregnancy.

Although stress has been studied in association with response to other vaccines including, but not limited to, hepatitis B ⁸ and pneumococcal pneumonia ⁹ assessment of antibody response to influenza vaccination is an ideal model for exploring stress and immune function during pregnancy. As noted, this vaccination that is recommended to pregnant women ¹⁰. Furthermore, the effectiveness of influenza vaccination in pregnant women has important health implications; influenza is more likely to result in serious medical complications among pregnant women than the general population. Relatedly, pregnant women are more likely to undergo hospitalization as a result of influenza than non-pregnant individuals of similar age. Therefore, understanding the effects of stress on response to this particular vaccine has important implications for potentially severe health outcomes. **The primary goal of this investigation is to examine whether pregnant women who report greater life stress show poorer antibody responses to influenza vaccination measured at one month post-vaccination and poorer antibody transfer to the neonate as measured in cord blood at the time of delivery. This study will also examine the role of obesity in these relationships. It is predicted that obesity will exacerbate effects of stress, resulting in the poorest outcomes in women with high stress and obesity.**

III. PROCEDURES

A. Research Design

The current study is designed to evaluate the relationship between psychosocial factors on one hand and antibody responses to influenza vaccination on the other. Participants will complete two study visits: pre-

vaccination and one month post-vaccination. Maternal a maternal serum sample will be collected by hospital staff during the hospital stay at the time of delivery and we will obtain a sample of cord blood. Cord blood is standardly collected and stored following every delivery at OSUMC. If the sample is not needed for medical reasons, it is discarded after a few days. We will obtain samples that would otherwise be discarded. If maternal serum is not collected at the time of hospital stay due to error in coordinating with hospital staff, we will arrange for a serum sample to be collected at the participant's home, a visit to our laboratory or CRC, or we will coordinate with the woman to collect this sample at the time she nexts visits her physician for a post-partum visit. If cord blood is not available from the hospital due to not being collected at delivery or used for testing purposes for infant care, we will arrange for infant blood to be collected by heel stick at the participant's home, a visit to our laboratory or CRC.

B. Sample

Pregnant women ages 18 and older will be recruited. As a part of routine care, pregnant women are encouraged to receive influenza vaccination. Women will primarily be recruited at their regular prenatal or gynecology visits at McCampbell Clinic. Those who are interested will be asked questions related to inclusion/exclusion criteria (i.e. age, health conditions, medications, and fetal health) to determine if they are eligible. Participant medications and health status (e.g., presence of chronic health conditions) will also be determined via chart review to confirm eligibility. Eligible individuals will be consented and the study will be described verbally to them.

Inclusion criteria for participants are adult (18 years and older) pregnant women who choose to have the influenza vaccination and who give informed consent. Exclusion criteria are fetal anomaly, health conditions or medications with a major immune component (e.g., arthritis, cancer, lupus) and inability to give informed consent.

Participants will be recruited from the prenatal clinic and general gynecology clinic at McCampbell Hall, OSU. Participants will also be recruited through flyers at other Ob/Gyn clinics and advertisements in local newspapers and campus newsletters (e.g., OSU Today) and ads posted online (e.g., on Campus newsletters; Stressandpregnancy.osumc.edu and other relevant websites for advertising/recruiting including ResearchMatch.org). Study visits will be completed at McCampbell Clinic, the OSU Clinical Research Center at Dodd Hall, or at [name] clinical laboratory at the Institute for Behavioral Medicine Research. If women are unable to travel to OSU for study visits (e.g., due to child care obligations), they may be given the option, funding permitting, of having a nurse or phlebotomist visit their home to complete follow up visits. (All Visit 1s will be conducted at either McCampbell Clinic or the CRC as this study visit requires the administration of the influenza virus vaccine).

C. Vaccination/ Measurement / Instrumentation

Influenza Vaccination. Each woman will be administered a standard influenza vaccine produced by GlaskoSmithKline or SanofiPasteur as available from the OSU Pharmacy which supplies McCampbell Clinic. The vaccine will be administered by a clinic nurse or a Clinical Research Center nurse. Each .05mL dose contains 45 µg of hemagglutinin of each of virus strain. All women vaccinated during the same influenza season will receive the vaccine from the same manufacturer and same lot whenever possible.

Serum samples. At each visit, whole blood will be collected into vacutainer tubes while the subject is in a seated position. Samples will be immediately centrifuged and placed in freezer storage until analysis. These samples will be stored at the laboratory of [name].

Self-report Measures. Questionnaire measures will be used assess how psychosocial factors (including stress, mood, and social support) relate to immune parameters of interest. Each of the following will be completed at one or more study visit.

The **Center for Epidemiological Studies Depression Scale (CES-D)** has been used extensively as a brief measure of depressive symptomatology ^{11,12}. Studies have shown acceptable test-retest reliability and excellent construct validity ¹². The 10-item version of the **Perceived Stress Scale (PSS)** will be used to measure the subjective experiences of stress and coping with stress using the past month as timeframe ¹³. **Parental Attitudes** regarding happiness about pregnancy have been associated with birth weight ¹⁴. Two questions adapted from the National Survey for Family Growth will be used in the current study ¹⁵. Each participant will be asked to describe how she felt about her pregnancy at the moment of discovery from 1 to 10, with 1 signifying unhappiness and 10 signifying happiness. Each participant will also rate her perception of her partner's happiness. This measure will be given to pregnant women only. The **Perceived Social Support Scale (PSSS)** will be used to assess support from family, friends, and a significant other. The **Prenatal Life Events Scale (PLES)** will be used to assess major life events occurring in the past year. This measure is appropriate for pregnant and nonpregnant women. The **Prenatal Health Behavior Scale** will be used to assess health behaviors including health eating, unhealthy eating, vitamin use, smoking, and exercise. This scale is appropriate for pregnant as well as nonpregnant women. The **Pregnancy Distress Questionnaire (NUPDQ)** will be used to assess anxiety about pregnancy, childbirth, and the strains of an additional child. This questionnaire will be completed by pregnant women only. The **Life Difficulties** questionnaire will be used to measure economic strain and living difficulties among both pregnant and nonpregnant women. The **Pittsburgh Sleep Quality Index (PSQI)** will be used to measure subjective sleep quality. We will assess **Fatty Acid** consumption via questionnaire assessing fish intake and fish oil supplement usage.

D. Detailed Study Procedures.

The following is the description of study procedures as provided to participants in the informed consent:

Visit 1 will take 60-90 minutes. You will answer questionnaires about your health, health behaviors, stressful life events, mood (e.g., anxiety and depressive symptoms), and social support. These include questions about positive and negative interactions with your friends/family as well as questions regarding stressful or traumatic events you may have experienced growing up. You will have 35 mL of blood drawn. Finally, you will receive an influenza virus vaccination (flu shot).

Visits 2 will take about 30 minutes and will occur one month after Visit 1. You will answer questions about your recent health behaviors, life stress, and mood and have 30 mL of blood drawn.

During your hospital stay at the time of the delivery of your baby, hospital staff will obtain a 30mL blood sample for our study. If this sample is not collected during your hospital stay, or if you do not deliver in a hospital, we will schedule a visit to your home or at our office soon after your delivery at a time that is convenient for you in order to collect this blood sample.

Finally, cord blood is standardly collected at every delivery at OSUMC. If it is not needed for medical reasons, it is discarded after a few days. If you deliver at OSUMC and your baby's cord blood is not needed for medical reasons, it will be given to our study personnel rather than being thrown away. If cord blood is not available for your baby, we will schedule a visit to our office soon after your delivery at a time that is convenient for you, in order to collect this blood sample. If you cannot come to our office, we will work with you to schedule a visit to your home. This blood sample will be collected from your baby by heel stick which is similar to a finger stick in adults.

Also, after your delivery, researchers will access your medical records to obtain the following information related to your pregnancy: your date of delivery, the birth weight and sex of your baby, how much weight you gained during your pregnancy, your blood pressure at clinic visits, the results of your clinical screenings for sexually transmitted diseases, and whether you had any complications during pregnancy or delivery.

Use of REDCap

We will use REDCap Survey for the purposes of online screening of participants. In the future, we may also use REDCap Database for collection and maintenance of study data. Data collected from enrolled participants is currently collected via teleform. The OSU CCTS Research Informatics Services Core will be used as a central location for data processing and management of data obtained via REDCap Survey and, if utilized in the future, REDCap Database. Vanderbilt University, with collaboration from a consortium of institutional partners (including OSU) and the NIH National Center for Research Resources, has developed a software toolset and workflow methodology for electronic collection and management of research and clinical trial data. REDCap (Research Electronic Data Capture) data collection projects rely on a thorough study-specific data dictionary defined in an iterative self-documenting process by all members of the research team with planning assistance from the CCTS Research Informatics Services Core. As part of the data dictionary development process, individual fields can be denoted as "identifiers". When exporting a de-identified dataset, these variables are omitted. Additionally, the data export tool also allows for the shifting of dates for a limited data set export. REDCap provides a secure, web-based application that is flexible enough to be used for a variety of types of research, provides an intuitive interface for users to enter data and has real time validation rules (with automated data type and range checks) at the time of entry. It offers easy data manipulation with audit trails and ad hoc reporting functionality for reporting, monitoring and querying patient records, and an automated export mechanism to common statistical packages (SPSS, SAS, Stata, R/S-Plus). REDCap is 21 CFR Part 11 capable. Currently, REDCap installations support electronic signatures by positively identifying the user through a unique username and password combination. The provisioning of accounts and user access to specific database(s) is integrated with the OSU Medical Center LDAP authentication service, and the provisioning of access and specific user rights are managed by CCTS staff.

E. Data Analysis

Analysis of influenza antibody titers. Antibody titers will be determined using an ELISA for the complete vaccine and each of the HA proteins included in the vaccine in the given year. Briefly, 96-well plates will be coated overnight at 4°C with vaccine (0.9 mg/ml) or purified HA protein (0.3 mg/ml), washed, and incubated 2 hr at 37°C; serum dilutions prepared in phosphate-buffered saline supplemented with 10% fetal bovine serum will then be added. Plates will be re-washed and goat anti-human IgG antibody and then alkaline phosphatase conjugate will be added and plates will be incubated 2 hr at 37°C. The secondary antibody will be detected using Sigma 10 phosphatase substrate tablets (Sigma) in diethanolamine buffer and absorbance was read at 405 nm. Titers were determined by identifying the serum dilution at which the titration curve became asymptotic.

Statistical Considerations.

Sample size calculation.

Sample size was based on ≥80% power to examine each hypothesis. Although Holm's stepdown procedure will be used in analyses, the more conservative Bonferroni adjustment was used for calculating sample size. For testing associations of composite stress and obesity with maternal antibody responses (Aim 1), our analyses will focus primarily on A/H1N1 and secondarily on influenza B; a 2009 meta-analyses concluded that responses to A/H3N2 strains are generally not susceptible to stress.[10] A

sample size of 60 in a given year will provide $\geq 90\%$ power to detect an odds ratio of 0.4 for 4-fold antibody increase for one SD increase in composite stress, at the Bonferroni-adjusted significance level $\alpha=0.025$. A sample size of 180 across 3 years will provide $\geq 82\%$ power to detect an odds ratio of 0.38 for obese vs. non-obese, also at $\alpha=0.025$. These effect sizes are shown in our preliminary data. We will have $\geq 80\%$ power to detect these effects for influenza B, assuming similar effect sizes. For testing associations of composite stress and obesity with cord blood antibody levels (Aim 2), a sample size of 60 in a given year will provide $\geq 80\%$ power to detect an odds ratio of <0.45 for adequate cord blood antibody level for one SD increase in composite stress, at $\alpha=0.025$. A sample of 180 across 3 years will provide $\geq 80\%$ power to detect an odds ratio of 0.4 or lower for adequate cord blood antibody level in newborns from obese versus non-obese mothers, at $\alpha=0.025$.

Statistical Analyses.

Specific Aim 1. Effects of stress on maternal antibody responses will be tested independently for each vaccination year. Thus, our data will provide valuable data regarding the extent to which effects of stress are consistent and reproducible across flu seasons. We will test the association between obesity and maternal antibody responses using data across all three vaccination years. The primary and supporting endpoints will be the same as above. The independent variable will be obesity status. A secondary analysis will explore the interaction between obesity and stress; these analyses will focus on depressive symptoms and the composite stress measure (CES-D, PSS, and STAI). We expect that stress and obesity will interact, with more pronounced effects of obesity among the highly stressed. Although the study is not specifically powered for the detection of interaction effects, based on our preliminary findings we expect to obtain useful estimates.

Specific Aim 2. The primary analysis will be logistic regression testing whether stress and obesity are associated with attenuated cord blood antibody levels. The primary endpoint will be adequacy of cord blood antibody level (yes/no), with an adequate antibody level defined as a serum HAI antibody titer > 40 . The same models will be used as described in Specific Aim 1, except for the change in dependent variable. A supporting analysis will test cord blood antibody levels as a continuous measure. Linear regression models will be used to test this supporting outcome, using the same independent variables as the logistic regression models.

Secondary mediational analyses will examine four potential pathways linking stress and obesity with low cord blood antibody titers: 1) the magnitude of maternal response at one month post-vaccination, 2) the maintenance of maternal antibody levels over time (maternal antibody at one month post-vaccination / maternal antibody at delivery) controlling for weeks from vaccination to delivery, 3) efficiency of antibody transfer (ratio of maternal antibody at time of delivery / newborn antibody level), and 4) the frequency of preterm birth (expected to be 15% overall). We expect factors 1 & 3 to exert the greatest effects. Our study is powered to detect overall effects of maternal stress and obesity on newborn antibody levels, but is not powered to detect the relative influence of each of these specific pathways. However, these analyses will provide a critical foundation for future studies in this line of investigation which will include this focus.

We do not expect racial differences in Aim 1. Due to higher rates of preterm birth in Blacks than Whites (18% vs 12%), this pathway is likely to contribute more strongly to the association between stress and lower cord blood titers for Blacks. We will use two approaches to examine effects of race: 1) inclusion of race as a predictive variable and 2) testing the secondary analysis model above separately for Blacks and Whites.

References

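### Earlier influenza vaccination, this season or last, is neither screened for, recorded nor modelled, although it can affect both primary endpoints

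*Combined protocol and SAP*

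**What the plan says.** Section III.B (Sample) screens with "questions related to inclusion/exclusion criteria (i.e. age, health conditions, medications, and fetal health"), and the list is introduced by 'i.e.', so it reads as complete. The chart check is described thus: "Participant medications and health status (e.g., presence of chronic health conditions) will also be determined via chart review to confirm eligibility". The only inclusion criterion that touches the vaccine is that participants are "pregnant women who choose to have the influenza vaccination and who give informed consent". The exclusions are stated in one sentence: "Exclusion criteria are fetal anomaly, health conditions or medications with a major immune component (e.g., arthritis, cancer, lupus) and inability to give informed consent". None concerns an earlier dose. The same section says "As a part of routine care, pregnant women are encouraged to receive influenza vaccination", so the study vaccine is also background care.

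The questionnaires in section III.C name no vaccination item. The health behavior scale "will be used to assess health behaviors including health eating, unhealthy eating, vitamin use, smoking, and exercise". The post-delivery record extraction in section III.D covers delivery date, birth weight, infant sex, weight gain, blood pressure, sexually transmitted disease screening and complications.

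In section III.E, the sample size text for Aim 1 uses "an odds ratio of 0.4 for 4-fold antibody increase for one SD increase in composite stress". The Aim 2 primary endpoint is a cord HAI titer above 40, yes or no. The only adjustment variables named are race and, for the antibody maintenance pathway, weeks from vaccination to delivery. Blood is drawn at Visit 1 before the shot, but no model names that titer as a covariate.

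**The concern.** Stress and obesity are observed here, not assigned, so the comparison depends on measuring other determinants of the outcome. Earlier influenza vaccination is a likely one, and it bears on the two primary endpoints in different ways. A fold-rise endpoint penalises a high starting titer; an absolute threshold rewards it. The same unrecorded variable can therefore lower the response rate in Aim 1 and raise the adequacy rate in Aim 2, and results that disagreed between the aims could not be separated from vaccination history.

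The two kinds of earlier dose raise different problems. After a dose in the same season, Visit 1 is no longer a baseline, and the titer measured there may itself be a response to vaccine. A dose last season leaves Visit 1 a true baseline, but possibly a raised one. The second is the more likely in this sample. History that is not collected at enrolment cannot be reliably filled in later.

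**Working it through.** **Plan's own figures.** Power for one standardised covariate in logistic regression is Φ(√(n·P·(1−P))·|ln OR| − z), with z = 2.241 for two-sided α = 0.025. The response rate P and the sidedness are not given; P = 0.5 and two-sided are assumed.
- Aim 1 stress, n = 60, OR 0.40: Φ(3.873 × 0.916 − 2.241) = Φ(1.307) = 90.4%. The plan says at least 90%.
- Aim 2 stress, n = 60, OR 0.45: Φ(3.873 × 0.799 − 2.241) = Φ(0.851) = 80.3%. The plan says at least 80%.
- Aim 1 obesity, n = 180, OR 0.38, 60% response if not obese: 81.6% with 40% obese and 83.3% with 50% obese. The plan says at least 82%.

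**Case A: earlier vaccination unrelated to stress.** Assumed: 20-60% previously vaccinated; odds ratio 0.10-0.25 for a 4-fold rise and 4-10 for a cord titer above 40, vaccinated v not. A logistic model on a large simulated sample, leaving vaccination out, gives a marginal odds ratio that is put back into the power formula.
- Aim 1: OR 0.40 becomes 0.42-0.49; power falls from 90% to 86%-60%.
- Aim 2: OR 0.45 becomes 0.47-0.53; power falls from 80% to 75%-46%.

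Not all of that fall comes from the omission. In the worst Aim 1 case (60% vaccinated, OR 0.10) the fitted odds ratio is 0.485 and the overall response is 27.1%, so √(60 × 0.271 × 0.729) = 3.443. The lower response rate alone gives Φ(3.443 × 0.916 − 2.241) = 82%. Adding the attenuation gives Φ(3.443 × 0.724 − 2.241) = 60%. A covariate addresses only the step from 82% to 60%, and only part of it, because adjustment restores the odds ratio but also widens its standard error.

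**Case B: two-group contrast such as obesity.** Assumed: 4-fold response 60% without and 30% or 45% with last season's vaccine; 60% vaccinated in one group and 40% in the other; no true effect.
- With 30%: 0.6 × 0.30 + 0.4 × 0.60 = 0.42, against 0.4 × 0.30 + 0.6 × 0.60 = 0.48. OR = (0.42/0.58)/(0.48/0.52) = 0.78.
- With 45%: 0.51 against 0.54. OR = (0.51/0.49)/(0.54/0.46) = 0.89.
- With the groups reversed: 1.27 and 1.13.

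With a within-stratum odds ratio of 0.40, the exposed responses become 37.5% (from 60%), 14.6% (from 30%) and 24.7% (from 45%). The crude odds ratio is then 0.34-0.36 if the exposed group was vaccinated more, and 0.46-0.55 if less.

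For scale, with 72 obese and 108 non-obese women (40% obese, assumed), the standard error of the log odds ratio is √(1/(72 × 0.42 × 0.58) + 1/(108 × 0.48 × 0.52)) = 0.307. The larger null bias is |ln 0.784| = 0.243, or 0.8 standard errors.

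**Per SD of stress.** If the two groups were halves of a normal stress score, their means would lie about 1.6 SD apart. Then 0.243/1.6 = 0.152 and 0.120/1.6 = 0.075, which are odds ratios of roughly 0.86 and 0.93 per SD. With a standard error of 1/√(60 × 0.25) = 0.258, that is at most 0.6 standard errors. Simulating the link directly (earlier vaccination related to stress with OR 1.5 or 0.67 per SD, ranges as in case A) gives spurious odds ratios of about 0.82-1.23 in either aim. Rejection in one direction is then 2.6%-6.0% instead of 1.25%.

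**The case against.** Several points on the other side stand.

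- A same-season earlier dose is unlikely. Women must choose the vaccine and receive it at Visit 1, and recruitment is mainly at regular visits to a clinic supplied with it. That does not exclude the case, because recruitment also uses other clinics, newspapers and websites.
- The Visit 1 serum partly captures last season's exposure, since a raised start is the mechanism. It does so only if a model uses it, and none is said to. It also cannot tell last season's vaccine from infection or from a dose weeks before.
- Directional bias needs earlier vaccination to differ by stress or obesity, and the documents say nothing on that.
- Later chart lookup or recall might recover some history, though less reliably, and the listed record items do not include it.

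Two stronger readings are tempting. A reader might infer that Aim 2 miscounts earlier vaccine as good transfer. The documents do not support this: the stated aim and endpoint are the newborn's antibody level, and antibody from an earlier dose is real cord antibody. Transfer efficiency is a separate maternal-to-newborn ratio, with background antibody in both terms. A reader might also infer that the power statements are wrong. They are not shown to be: the stress figures reproduce at a 50% response rate, and the Aim 1 obesity figure is reachable on favourable inputs.

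**Conclusion.** The omission is certain: no part of the plan asks about, records or adjusts for influenza vaccination earlier in the season or in the previous one. Its consequence is conditional. If earlier vaccination is unrelated to the exposures, the odds ratios move toward 1 and power is lost. If it is related, they are confounded, and the study could not tell in which direction. It would go too far to say that the stress and obesity effects are biased.

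For a contrast such as obesity, the illustration moves a null odds ratio to 0.78-0.89 or 1.13-1.27. Per SD of stress the shift is smaller. Every input on vaccination share and effect is an assumption, since the documents give none. The gap should be closed because the data are cheap at enrolment and each year's stress analysis rests on only 60 women.

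**What to change.** Add two items to the existing screening questions and chart review.

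1. Influenza vaccine already received this season. Such women are not enrolled in the study, or are excluded from the primary analyses if this is found later, because no pre-vaccination sample exists for them.
2. Influenza vaccine received last season: yes, no or unknown, with the source of the information.

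Prespecify item 2 as a covariate in the stress and obesity models of both aims, with a sensitivity analysis that also adjusts for the Visit 1 titer. Do not report odds ratios within vaccination levels for the per-year stress analyses: at 40-60% vaccinated, 60 women split into strata of about 24-36. At most, show them descriptively for the pooled obesity analysis.

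The cost is two form items, one extra model term, a few otherwise eligible women lost and some recall error. Discovery of a same-season dose after enrolment will be incomplete, so the screening question matters more than the later exclusion.

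### With 60 women, two-sided α of 0.025 and 50% response, power for the stress effects is about 80–85% and 68–74%, not the stated ≥90% and ≥80%

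*Combined protocol and SAP*

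**What the plan says.** The power statements are in section III.E, Sample size calculation. The general criterion is "Sample size was based on ≥80% power to examine each hypothesis". Holm's procedure is planned for the analysis, but "the more conservative Bonferroni adjustment was used for calculating sample size", which gives α=0.025.

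Two claims concern stress with 60 women in a given year:

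- Aim 1 (maternal response): at least 90% "power to detect an odds ratio of 0.4 for 4-fold antibody increase for one SD increase in composite stress".
- Aim 2 (cord blood): at least 80% "power to detect an odds ratio of <0.45 for adequate cord blood antibody level for one SD increase in composite stress".

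Under Statistical Analyses, Specific Aim 1 says: "Effects of stress on maternal antibody responses will be tested independently for each vaccination year". So 60, not 180, is the sample size that counts for stress. Specific Aim 2 says: "The primary analysis will be logistic regression testing whether stress and obesity are associated with attenuated cord blood antibody levels". It adds: "The same models will be used as described in Specific Aim 1, except for the change in dependent variable". Logistic regression is therefore the planned model for both claims.

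The plan does not say whether 0.025 is one-sided or two-sided. It also gives no expected rate of four-fold rise or adequate cord level, no power formula, no choice among Wald, score and likelihood-ratio tests, and no distribution for the stress score.

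**The concern.** Sixty binary outcomes are few for 90% power at a two-sided 0.025 level, even with an odds ratio of 0.4 per SD. The usual quick formula for a continuous covariate uses the outcome variance under the null hypothesis, p(1−p). When the log odds ratio per SD is 0.8 to 0.9, women with high or low scores have response probabilities far from the average and carry less information than the formula assumes, so it is optimistic.

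The per-year stress tests are meant to show whether stress effects reproduce across flu seasons. If per-year power is overstated, a chance miss in one season is more easily read as real inconsistency. For cord blood, the plan's own 80% criterion may also fail at the odds ratio it names.

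**Working it through.** **Inputs from the plan:** n = 60; α = 0.025; odds ratios 0.40 and 0.45 (the boundary of the Aim 2 claim) per SD; logistic regression.

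**Assumptions, because the plan gives no values:** two-sided test (z = 2.2414); overall response p of 50%, 40% or 30%; roughly normal stress score, standardised in the sample; all 60 women evaluable.

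**Step 1. Can the stated figures be reproduced?** The simple formula is

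power = Φ( √(n·p·(1−p)) × |ln OR| − z ).

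At p = 0.5, √(60 × 0.25) = 3.873.

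- OR 0.40: 3.873 × 0.9163 − 2.2414 = 1.307, so power is 90.4%. The n for 90% is 59.1.
- OR 0.45: 3.873 × 0.7985 − 2.2414 = 0.851, so power is 80.3%. The n for 80% is 59.6.

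Both required sizes round up to 60. This may be how the figures were obtained, but that is an inference, since the plan names no formula. Because p(1−p) is largest at 50%, these are the formula's best values. At 40% it gives 89.2% and 78.5%; at 30%, 84.4% and 72.3%. It reaches 90% for OR 0.40 only when response is about 44–56%, and 80% for OR 0.45 only at about 46–54%.

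**Step 2. What does the planned test deliver?** Simulated power, 40,000 datasets per cell, n = 60, two-sided 0.025, shown as Wald / score / likelihood ratio:

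| Response | OR 0.40 (stated ≥90%) | OR 0.45 (stated ≥80%) |
|---|---|---|
| 50% | 80.8 / 83.9 / 85.1% | 68.2 / 72.2 / 74.0% |
| 40% (assumed) | 78.3 / 81.8 / 83.1% | 66.0 / 70.1 / 71.9% |
| 30% (assumed) | 71.8 / 76.0 / 77.8% | 59.2 / 63.9 / 65.9% |

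Rejection under the null at nominal 0.025 was 0.019 (Wald), 0.025 (score) and 0.029 (likelihood ratio). The score test is therefore the one closest to its nominal size.

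**Step 3. What effect is detectable with 60 women?** At 50% response (25,000 datasets per cell), power is 80.4 / 83.5 / 84.8% at OR 0.40, 76.2 / 79.7 / 81.0% at 0.42, and 70.9 / 74.8 / 76.5% at 0.44. Power of 80% is reached at an odds ratio of about 0.40–0.42.

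**Step 4. Other readings at n = 60.**

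| Reading | OR 0.40 | OR 0.45 |
|---|---|---|
| One-sided 0.025, 50% response | 89–91% | 80–83% |
| One-sided 0.025, 40% response | 87–90% | 78–81% |
| One-sided 0.025, 30% response | 83–86% | 72–76% |
| Two-point score split 30/30, two-sided, 50% response | 89% | 79% |

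Two-sided 0.05 is the most Holm's procedure can give, and then only if the companion hypothesis is always rejected. Its values equal the one-sided 0.025 values to three decimals.

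**For scale only:** at 50% response and two-sided 0.025, 90% power for OR 0.40 corresponds to about 70–75 women, and 80% for OR 0.45 to about 68–74.

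**The case against.** The strongest reply is that nothing was miscalculated. A standard planning formula gives 90.4% and 80.3%, and both claims lead to exactly 60 women. That stands as far as it goes: the problem looks like an approximation used where it is inaccurate, at its best-case response rate, and not a slip in the sums. It does not make the stated powers true of the planned test.

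Other points have partial force:

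- **Sidedness.** The objectives are worded directionally ("Our goal is to determine whether greater life stress and obesity reduce 1) antibody responses to the flu shot in women"), and one-sided 0.025 roughly supports both figures at 50% response. But no one-sided test is stated, and at 30% response both figures fail even so.
- **Choice of test.** The low ends of the ranges come from the Wald test, which spends less than its nominal α. With the score test the gaps at 50% response are about 6 points (83.9% against 90%) and 8 points (72.2% against 80%). They remain.
- **Holm.** Actual power will exceed the 0.025 values. The plan nevertheless attaches both claims to 0.025, and the gain depends on the other hypothesis being rejected.
- **Wording of the Aim 2 claim.** It covers odds ratios below 0.45, so 0.45 is its weakest point. At 0.44, power is still only 71–77%.
- **Score distribution.** An evenly split two-point score nearly restores the figures, but the composite is built from CES-D, PSS and STAI and will not behave that way.
- **Response rates.** The 40% and 30% rows are assumptions. The shortfall is already present at 50%.

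**Conclusion.** The concern holds. On a two-sided reading of 0.025, with a roughly normal score, 60 evaluable women and 50% response, the planned logistic regression has about 80–85% power for OR 0.40 and 68–74% for OR 0.45. The chance of missing a true OR of 0.40 is then about 15–19%, where the text implies at most 10%. For OR 0.45 it is about 26–32%, where the text implies at most 20%. Response rates further from 50% widen the gap.

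The practical harm is smaller than the gap in the text. Under Holm the miss rates could fall, though to no less than about 9–11% and 17–20%. The general 80% criterion is met for OR 0.40 at 50% response. It fails for cord blood stress odds ratios between about 0.42 and 0.45. The conclusion depends on the two-sided reading; a declared one-sided test would largely remove it at 50% response, but not at 30%.

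**What to change.** Rewrite the two n = 60 stress statements in the Sample size calculation paragraph:

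- Give power from simulation of the planned logistic model: about 80–85% for OR 0.40 and 68–74% for OR 0.45 at two-sided 0.025 and 50% response. Alternatively, give the odds ratio detectable with 80% power, about 0.40–0.42. Drop the ≥ signs.
- State whether 0.025 is one-sided or two-sided. If one-sided testing was intended, say so and give those values.
- State the rates of four-fold rise and adequate cord level that were used, and show power over a range, for example 30–50%.
- Name the test and the power method, and say that 60 means evaluable women.

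The cost is one rewritten paragraph and less favourable stated powers. No change to enrolment, design or analysis is needed.
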